3.1.3 Day 1 (Visit 2)

Patients will arrive at the CRC either the evening before or in the morning of Day 1 as directed by CRC staff. At this time patients will be reassessed with regard to the study eligibility criteria and begin Day 1 study procedures as outlined in Table 1. Patients who still meet the eligibility criteria will be randomized at this time.

All study drug will be administered by CRC personnel. Esomeprazole as either 5 mg or 10 mg capsules (for patients who weigh 8 to <20 kg) or as either 10 mg or 20 mg capsules (for patients who weigh \geq 20 kg) will be dosed according to the randomization schedule. The dose will be administered 1 hour prior to breakfast (for patients who are aged 1-5 years) or 2 hours prior to breakfast (for patients who are aged 6-11 years).

Patients will be discharged from the CRC after the 6-hour post dose PK sample collection if they have been able to tolerate at least one meal after the fast and after being assessed by study personnel and found to be stable.

Please refer to the Table 1 and Table 5 for the timing and detailed descriptions of the assessments and procedures to be performed on Day 1.

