3.1.4 Follow-up (Visit 3)

Patients will return to the CRC for a follow-up visit preferably at 7 days after study drug administration. If necessary this visit may be scheduled up to 14 days after study drug administration.

Please refer to Table 1 for a detailed description of the assessments and procedures to be performed during the follow-up visit.

Clinical Pharmacology Study Protocol Drug Substance Esomeprazole magnesium Study Code D9614C00007 Date

- a A minimum of 6 evaluable patients per dosing group will be required. Refer to Table 4.
- b Please refer to Table 2

Assessment/Procedure	Screening Period (Within 21 days prior to randomization (Visit 1)	Day 1 (Dosing and PK Day) (Visit 2)	Follow-Up Visit (7-14 days after Day 1) (Visit 3)
Informed consent/assent	X		
Demographics	X		
Review inclusion/exclusion	X	X	
Full Medical History including surgical history	Х		
Complete physical exam	X		X
Vital signs ^a	X	X	Х
Concomitant medications	Х	X	Х
Clinical chemistry, hematology, urinalysis	Х		X
Urine pregnancy test ^b		X	
Endoscopic examination ^c	X		
Randomization		X	
Study drug administration ^d		X	
Blood samples for esomeprazole concentration ^e		X	
Meals ^f		Х	
Adverse Events		X	Х
Serious Adverse Events	X	Х	X

a. Blood pressure and pulse will be evaluated in the seated position. Vital signs will also include respiratory rate and either oral, rectal or tympanic temperature evaluations. On Study Day 1 vital signs evaluations will occur prior to dosing.

- b. A urine pregnancy test will be required for all post-menarchal females on Day 1 prior to study drug administration.
- c. Endoscopy will be performed during the screening period unless the patient has had a prior endoscopy within 14 days prior to enrollment (Visit 1) into the study.
- d. Study drug will be administered by CRC personnel.
- e. Blood samples (0.8 mL-1mL each) will be collected as follows: pre-dose, 0.5, 1.0. 1.5, 2.0, 3.0, 4.0 and 6 hours post dose.
- f. A light low-fat breakfast will be served 1-hour post dose (for patients 1-5) and 2 hours post dose (for patients 6-11) following study drug administration. Lunch will be provided following the 4-hour post dose PK sample collection.

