3.4.4 Blinding and procedures for unblinding the study (Not applicable)

3.4.5 Concomitant medication

Concurrent therapies with PPIs are not permitted within 7 days prior to Day 1 through completion of all study procedures on Study Day 1.

Concurrent therapies with H_2RAs are not permitted within 3 days prior to Day 1 and through completion of study procedures on Study Day 1.

Concurrent therapies with over the counter (OTC) antacids are not permitted within 24 hours prior to Day 1 until completion of study procedures on Day 1.

Any medication, which is considered necessary for the subject's safety and well-being, may be given at the discretion of the investigator(s). The administration of all medication (including investigational products) must be recorded in the appropriate sections of the case report form (CRF).

Concomitant use of the following medications during the study is prohibited:

- Bismuth-containing antacids
- Barbiturates
- Warfarin-anticoagulants
- Narcotics
- Antineoplastic agents
- H₂RAs
- Sucralfate
- Anti-emetics
- Systemic steroids (oral or intravenous)

- Pro-motility drugs (ie, cisapride, metoclopramide)
- Macrolide antibiotics (ie, erythromycin)
- Prostaglandin analogs

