4.7.1 Adverse Events

4.7.1.1 Definitions

The definitions of adverse events (AEs), serious adverse events (SAEs) and other significant adverse events (OAEs) are given below. It is of the utmost importance that all staff involved in the study are familiar with the content of this section. The Principal Investigator is responsible for ensuring this.

Adverse event

An adverse event (AE) is the development of an undesirable medical condition or the deterioration of a pre-existing medical condition following or during exposure to a pharmaceutical product, whether or not considered causally related to the product. An undesirable medical condition can be symptoms (eg, nausea, chest pain), signs (eg, tachycardia, enlarged liver) or the abnormal results of an investigation (eg, laboratory findings, electrocardiogram). In clinical studies, an AE can include an undesirable medical condition occurring at any time, including run-in or washout periods, even if no study treatment has been administered.

Serious adverse event

A serious adverse event is an AE occurring during any study phase (ie, run-in, treatment, washout, follow-up), and at any dose of the investigational product, comparator or placebo, that fulfils one or more of the following criteria:

- Results in death
- Is immediately life-threatening
- Requires in-patient hospitalization or prolongation of existing hospitalization
- Results in persistent or significant disability or incapacity
- Is a congenital abnormality or birth defect
- Is an important medical event that may jeopardize the subject or may require medical intervention to prevent one of the outcomes listed above.

The causality of SAEs (ie, their relationship to study treatment) will be assessed by the investigator(s), who in completing the relevant case report form must answer "yes" or "no" to the question, "do you consider that there is a reasonable possibility that the event may have been caused by any of the following: study medication, other medication?" For further guidance on the definition of a SAE and a guide to the interpretation of the causality question, see Appendix B to the Clinical Pharmacology Study Protocol.

Note that SAEs that could be associated with any study procedure should also be reported. For such events the causal relationship is implied as "yes."

Other Significant Adverse Events (OAE)

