4.7.1.2 Recording of adverse events

Adverse events will be collected from the first dose of the investigational product until the follow-up visit. However, SAEs will be reported from the time when the informed consent is obtained through the follow-up visit. All SAEs will be recorded and immediately reported to the sponsor. The date of the final follow-up visit will be the last date when the investigator actively will ask for the AEs occurring during the study.

The following variables will be recorded for each AE in the CRF: verbatim, date when the AE started and stopped, action taken with regard to the investigational product, maximum intensity, outcome, causality and whether the AE constitutes and SAE or not.

Causality of non-serious adverse events will be assessed in the same way for SAEs. See Appendix B for further guidance.

Intensity will be assessed according to the following scale:

- mild (awareness of sign or symptom, but easily tolerated)
- moderate (discomfort sufficient to cause interference with normal activities)
- severe (incapacitating, with inability to perform normal activities)

It is important to distinguish between serious and severe AEs. Severity is a measure of intensity whereas seriousness is defined by the criteria in Section 4.7.1.1. An AE of severe intensity need not necessarily be considered serious. For example, nausea that persists for several hours may be considered severe nausea, but not a SAE. On the other hand, a stroke that results in only a limited degree of disability may be considered a mild stroke but would be a SAE.

All adverse events spontaneously reported by the volunteer and/or in response to the question "have you had any health problems since the previous visit?" or revealed by observation will be collected and recorded in the CRF. When collecting adverse events, the recording of the diagnosis (when possible) is preferred over recording a list of signs or symptoms (eg, upper gastrointestinal hemorrhage should be used rather than hematemesis, melena and anemia). However if a diagnosis is known and there are other signs or symptoms that are not generally part of the diagnosis, the diagnosis and each sign or symptom should be recorded separately.

Should a pregnancy occur, it must be reported in accordance with the procedures described in Section 8.4.

Adverse events will be coded by AstraZeneca staff at AstraZeneca R&D, Wilmington, Delaware, using the Medical Dictionary for Regulatory Activities (MedDRA).

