Following administration of equimolar doses, the S- and R-isomers are metabolized differently by the liver, resulting in higher plasma levels of the S- than of the R-isomer.

Excretion

The plasma elimination half-life of esomeprazole is approximately 1-1.5 hours. Less than 1% of parent drug is excreted in the urine. Approximately 80% of an oral dose of esomeprazole is excreted as inactive metabolites in the urine, and the remainder is found as inactive metabolites in the feces.

Special Populations

Geriatric

The AUC and C_{max} values were slightly higher (25% and 18%, respectively) in the elderly as compared to younger subjects at steady state. Dosage adjustment based on age is not necessary.

Pediatric

The pharmacokinetics of esomeprazole have not been studied in patients < 18 years of age.

Gender

The AUC and C_{max} values were slightly higher (13%) in females than in males at steady state. Dosage adjustment based on gender is not necessary.

Hepatic Insufficiency

The steady state pharmacokinetics of esomeprazole obtained after administration of 40 mg once daily to 4 patients each with mild (Child Pugh A), moderate (Child Pugh Class B), and severe (Child Pugh Class C) liver insufficiency were compared to those obtained in 36 male and female GERD patients with normal liver function. In patients with mild and moderate hepatic insufficiency, the AUCs were within the range that could be expected in patients with normal liver function. In patients with severe hepatic insufficiency the AUCs were 2 to 3 times higher than in the patients with normal liver function. No dosage adjustment is recommended for patients with mild to moderate hepatic insufficiency (Child Pugh Classes A and B). However, in patients with severe hepatic insufficiency (Child Pugh Class C) a dose of 20 mg once daily should not be exceeded (See **DOSAGE AND ADMINISTRATION**).

Renal Insufficiency

The pharmacokinetics of esomeprazole in patients with renal impairment are not expected to be altered relative to healthy volunteers as less than 1% of esomeprazole is excreted unchanged in urine.

Pharmacokinetics: Combination Therapy with Antimicrobials

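### Vital signs are a safety variable for a single dose, but no set is scheduled between the dose and the 7-14 day follow-up visit

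*Protocol*

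**What the plan says.** **Vital signs.** Table 1 (printed under Section 3.1.4) marks vital signs at screening, on Day 1 and at follow-up. Its footnote a adds: "On Study Day 1 vital signs evaluations will occur prior to dosing". Amendments 01 and 02 reprint the footnote unchanged, so it is current. Sections 6.2.1 and 6.4.2 list vital signs as a safety variable, and Section 6.4.4 plans descriptive statistics for them. Section 4.4.4 lets the investigator take extra readings, entered as unscheduled.

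**The Day 1 stay.** Under Section 3.1.3 the child leaves after the 6-hour sample, once a meal has been tolerated and "after being assessed by study personnel and found to be stable". The content of that assessment is not specified.

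**Elimination.** Appendix D, under Excretion: "The plasma elimination half-life of esomeprazole is approximately 1-1.5 hours". The same insert says pharmacokinetics were not studied below 18 years.

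**Adverse events.** Section 4.7.1.2: "Adverse events will be collected from the first dose of the investigational product until the follow-up visit". For serious events it continues: "However, SAEs will be reported from the time when the informed consent is obtained through the follow-up visit". The definition in Section 4.7.1.1 says that "an AE can include an undesirable medical condition occurring at any time, including run-in or washout periods". Section 3.4.5 imposes the washout: "Concurrent therapies with PPIs are not permitted within 7 days prior to Day 1", with 3 days for H2 antagonists.

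**The concern.** A vital-sign summary can speak to the acute tolerability of a single dose only if some readings are taken while the drug is present. As scheduled, one set is taken before any drug is given and the next a week or more later. The child is meanwhile at the centre for at least 6 hours, so the opportunity exists and is not used. At stake is the usefulness of one of the four listed safety components for secondary objective 3. An asymptomatic change in pulse or blood pressure in a child as young as 1 year would be found only if somebody chose to measure it. The package insert lists tachycardia and hypertension among possibly or probably related events with incidence below 1%, so the variable is not irrelevant to this drug.

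**Working it through.** The plan states no figure to reproduce. The check places the scheduled sets on the time axis of one dose.

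**1. Scheduled sets**

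| Set | Time relative to dose |
|---|---|
| Screening | up to 21 days before |
| Day 1 | before dosing |
| Follow-up | 7 to 14 days after, i.e. 168 to 336 h |

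Sets during the post-dose stay: 0 of 3. Blood draws in the same stay (Table 5): 8 − 1 pre-dose = 7.

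**2. Half-lives elapsed at follow-up**, n = t / t½, with t½ = 1 to 1.5 h (adult figure, assumed for children):
- day 7: 168/1.5 = 112 to 168/1.0 = 168
- day 14: 336/1.5 = 224 to 336/1.0 = 336

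The conclusion does not depend on the adult figure. With a half-life of 3 h, twice the upper value, day 7 is still 168/3 = 56 half-lives away. For day 7 to fall within 10 half-lives, the half-life would have to be 168/10 = 16.8 h, about 11 times the upper adult value (16.8/1.5 = 11.2).

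**3. What the stay covers.** Six hours span 6/1.5 = 4 to 6/1.0 = 6 half-lives and include the adult time to peak of about 1.5 h (Appendix D).

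**4. What an added set would see**, assuming single-exponential decline from a peak at 1.5 h:
- at 6 h, 4.5 h after the peak: 4.5/1.5 = 3 to 4.5/1.0 = 4.5 half-lives, so 2^−3 = 12.5% down to 2^−4.5 = 4.4% of peak
- at 3 h, 1.5 h after the peak: 1 to 1.5 half-lives, so 50% down to 2^−1.5 = 35% of peak

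A discharge set thus falls in the tail of plasma exposure, and an earlier one nearer the peak.

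**5. Do other provisions supply the data?**
- Section 4.4.4 readings are discretionary, so they arise selectively and cannot be summarised for all children.
- The Section 3.1.3 discharge check requires no named measurement or record.
- Section 4.7.1.2 records a vital-sign abnormality as an adverse event only if it meets a seriousness criterion, leads to discontinuation, or is judged clinically important. It must first have been measured.

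**6. Adverse events in the washout.** The Section 4.7.1.1 definition admits washout events, whereas Section 4.7.1.2 and Table 1 start non-serious collection at the dose. The standard question in Section 4.7.1.2 looks back to the previous visit, so if asked before dosing at Visit 2 it would elicit events outside that window. The gap is limited to non-serious events, in children who actually stop a PPI (7 days) or an H2 antagonist (3 days).

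**The case against.** The best defence is that safety does not rest on vital signs alone. Adverse events and serious adverse events are collected from the dose, the child is supervised through the 6-hour sample, and clinically important vital-sign abnormalities become adverse events. The study is descriptive, with about 6 evaluable children per group and no untreated arm, and readings taken beside repeated blood draws would be hard to attribute to the drug. Section 1.1 also describes pump inhibition as irreversible, so plasma half-life need not govern effect.

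Much of this stands. A reader might infer that exposure is not observed at all, or that objective 3 cannot be answered. The documents do not support either: the adverse-event component covers the exposure window. The attribution difficulty limits what added readings could show, but the planned summary has the same lack of a control arm and no reading during exposure. The irreversibility point is a fair caution against equating absence from plasma with absence of effect, but it does not make day 7 a measure of acute tolerability.

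On the washout, a reader might infer that harm from stopping treatment is invisible, or that rebound symptoms will be counted as drug effects. Serious events are reported from consent. Screening history and examination are recorded, an adverse event requires development or deterioration of a condition, and Appendix B has the investigator weigh time course and other causes. Rebound after stopping acid suppressants is not mentioned in the documents. The definition is permissive, and Table 1 agrees with Section 4.7.1.2 in separating the two start points, so the split looks deliberate.

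**Conclusion.** The point holds for vital signs. None of the three scheduled sets falls between the dose and the 7-14 day visit, which is 112 to 336 half-lives later on the adult figure and well beyond exposure under any plausible extension of it. The planned summary therefore compares states in which the study dose is essentially absent. This weakens one component of a secondary objective; it does not disable the safety assessment and does not touch the primary pharmacokinetic objective.

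The result rests on reading footnote a as the whole Day 1 schedule, which nothing else in the protocol contradicts, and on the adult half-life as an order of magnitude. The washout point is secondary: a difference in scope between a permissive definition and a consistent collection rule, worth aligning but not an error that biases the study.

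**What to change.** In Table 1 footnote a, add one recorded set of vital signs at the discharge assessment after the 6-hour sample, and summarise the change from the pre-dose set by weight group and dose. An earlier set is optional. It should avoid the timed draws and breakfast: in Table 5 the interval after the 3-hour draw is the first full hour between draws with no meal scheduled at its start for either age band.

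The cost is several minutes per child and set (about 5 minutes' rest and a 1-minute respiratory count under Section 4.4.3) and one more CRF line for each set. No visit or blood is added.

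Optionally, align Sections 4.7.1.1 and 4.7.1.2, for example by collecting all adverse events from consent and tabulating pre-dose and post-dose events separately. This costs some additional entries and would still miss any washout begun before consent.

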3.2 Rationale and risk/benefit assessment

3.2.1 Rationale for study design, doses and control groups

Physicians have limited options when considering treatment to alleviate GERD symptoms in pediatric patients aged 1-11 years old. Presently, there are only 2 approved PPIs available to treat Pediatric GERD, omeprazole (2-16 years) and lansoprazole (1-17 years). Adult studies have demonstrated a greater acid-suppressive capacity for esomeprazole against all other available PPIs but pharmacokinetic and safety data in the younger age groups is still needed.

In this study, the patient population will be comprised of 24 evaluable male and female patients aged 1 to 11 years old inclusive who have endoscopically-proven GERD (ie reflux esophagitis, erosive or non-erosive). Randomization will be stratified by weight as explained in Figure 1. At least 6 patients will be randomized into each of the 4 dosing categories see Figure 1. When at least 6 evaluable patients have been randomized per group, recruitment of patients for that group will be stopped. The sample size was selected based on the need to provide data sufficient to describe the PK profile for esomeprazole in this population.

Esomeprazole doses for this pediatric population were selected based on extensive work done with available omeprazole and esomeprazole data using appropriate modeling techniques and a thorough review of pediatric pharmacokinetic and pharmacodynamic literature (AstraZeneca Clinical Pharmacology Report, [name] 2003). The esomeprazole exposure (AUC) and the response (efficacy and safety) relationship in a pediatric population were established via comprehensive pharmacokinetic and population PK modeling analysis of the omeprazole data in pediatric and adult patients and the esomeprazole data in adult patients. Extrapolating the esomeprazole doses from adults to children was consistent with the FDA Guidance for Industry: Exposure-response relationships-study design, data analysis, and regulatory applications (April 2003). With the established exposure-response relationship and an assumption of 8 kg to 60 kg of body weight range for children in this age group (1 to 11 years of age inclusive), it is estimated that the dosing range of 5mg to 20mg will have a reasonable chance to show efficacy and limit unnecessary high exposure. The pediatric dosing rationale can be applied to the different age groups based on approximate weight as estimated in the standard growth curves. Ultimately, randomization is stratified by weight but the chosen dosing schedule can still be reconciled in most cases with the corresponding age groups.

Table 2 provides minimum and maximum dosages based on weight:

Age	Weight	Total Doses	Approximate dose in mg/kg
1 –11	\geq 8 kg and <20 kg	5 mg or 10 mg	(0.25 mg/kg - 0.6 mg/kg) or (0.5 mg/kg - 1.25mg/kg)
years	≥20 kg	10 mg or 20 mg	(0.5 mg/kg -1.0 mg/kg) for lowest weight patient

Table 2Dosing grid

AUC was chosen as the primary variable since it has been well established that the inhibition of acid secretion by esomeprazole is well correlated with the AUC of esomeprazole (Andersson, et al 2001).

3.2.2 Risk/benefit and ethical assessment

The findings from completed studies D9614C00099 and D9614C00094 did not show any major safety and/or tolerability issues with single daily doses of esomeprazole in the pediatric population in children aged 1-17 years of age inclusive with symptoms of GERD. During these studies there were few adverse events, no discontinuations due to adverse events, no deaths and 1 serious adverse event that was not considered to be treatment related. In addition, study D9614C00098 was designed to gain safety and tolerability information of single daily oral doses of esomeprazole over an 8-week period. The results of this study demonstrated that esomeprazole was safe and well tolerated in the study population of pediatric GERD patients aged 12-17 years inclusive. There were no deaths, no serious adverse events, and few discontinuations due to adverse events during this study.

Information provided from these 3 studies demonstrated that esomeprazole addresses the medical need to provide treatment of GERD in pediatric patients. The safety of esomeprazole for the short-term treatment of GERD symptoms has been established in the population studied. In addition, a significant reduction in the severity of GERD symptoms and improvements in the patients' quality of life were observed in study D9614C00098 (a double-blind non-placebo controlled trial).

The purpose of the current study is to gain additional pharmacokinetic data in patients aged 1 to 11 years inclusive who have endoscopic evidence of GERD and to assess the safety and tolerability in this age group.

This is a low risk study. All endoscopic procedures pertaining to this study population are part of the standard of care and none will be done solely for research purposes. There is an minimal risk with phlebotomy being performed during this study. The study drug has a strong safety profile. The study will not provide any direct benefit to the patients. However, at the end of the study, families of patients will receive vouchers that will allow for covering the cost of medical treatment for 8 weeks at the discretion of the investigator. Information concerning the disease state in the patient will be determined and this can aid in future treatment options.

